## **ii. Information required for full-scale RCT**

If we conclude that a full-scale RCT of Tai Chi for cLBP in older adults is feasible, we will calculate our sample size requirements using estimates of the standard deviations from large previous RCTs of other CIM interventions of older adults, accepted criteria for the minimum clinically important difference for the RMDQ (our primary outcome measure), standard levels of type I and type II errors, and dropout rates estimated from this study's follow-up rates.

We plan to analyze the data in the full-scale RCT using the recommendations from the RTF. Because most of the outcome measures they propose are relatively new, it is important for us to compute summary statistics for these measures (e.g., means, percentages) so that we can compare our population to others reported in the literature and so that we can identify issues with missing data, etc. Using data from this feasibility RCT, we plan to conduct preliminary analyses using the recommendations from the RTF (i.e., examine continuous outcomes, perform responder analyses [the proportion of study participants who achieve specific thresholds], and look at the cumulative distribution function for improvement by treatment group to see what challenges, if any, we encounter. Finally, we will also stratify patients in this study by the personal impact of cLBP on them. We will use the recommended Impact Stratification approach to see what the distribution would be in this population and whether sub-group analyses are likely feasible in the full-scale RCT.

## **iii. Preliminary Outcome Analyses**

Preliminary analyses will not be properly powered, but will alert us to potential analytic challenges in the full-scale trial. We will employ the analytic techniques we would propose in a full-scale trial. In our comparisons of treatments on the outcome measures, we will analyze outcomes from all follow-up time points in a single model, adjusting for possible correlation within individuals and treatment group cohorts using generalized estimating equations (GEE). Because we cannot reasonably make an assumption of constant or linear group differences over time, we will include an interaction term between treatment group and time point. We plan to adjust for baseline outcome value, gender, and age of analyses. The general form of the regression model will be:  $g(Y(t)) = \beta_0 + \beta_1 Baseline + \alpha_1 Trt + \alpha_2 Trt \times Time + \alpha_3 z + \varepsilon$ , where  $Y(t)$  is the response at follow-up time  $t$ , *Baseline* is the pre-randomization value of the outcome measure, *Trt* include a dummy variables for the Tai Chi group or the Comprehensive Health Education Control group, *Time* is a series of dummy variables indicating the follow-up times, and  $z$  is a vector of covariates representing other variables being adjusted for. (Note that  $\alpha_1$ ,  $\alpha_2$ , and  $\alpha_3$  are vectors.) The referent group in this model is the Usual Medical Care group. For binary and continuous outcomes, we will use appropriate link functions (i.e., logit for binary).

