### *2.2a. Long Term Goal of Research*

Our ultimate goal is to conduct an RCT to answer the practical question of whether Tai Chi is effective for relieving cLBP in older adults **when added to** Usual Medical Care. Our Standard dose of Tai Chi would be 12-week 2x/weekly series of Tai Chi classes (see Section 5 for further details and justification). Because Tai Chi requires ongoing practice, maintaining the practice is critical and so we would investigate the value of including an Enhanced Tai Chi group that receives Standard Tai Chi plus a 24 week maintenance period of progressively fewer classes: 6 weeks of weekly classes, 6 weeks of every other week classes and 12 weeks of monthly classes). All classes would be 60 minutes long. Participants would be asked to practice 15 minutes at home on all non-class days. The anticipated design of our full-scale trial is depicted on the next page (note that Usual Medical Care will be available to all study groups). We are unclear regarding the value of an Attention Control, which will be included in one of the cohorts of the feasibility RCT:

[figure not shown]
Our principal hypotheses would be:

H1: Tai Chi is superior to Usual Medical Care at 12, 26, and 52 weeks. (Primary time point would be 12 weeks).

H2: Enhanced Tai Chi (standard + maintenance) is superior to Standard Tai Chi at 26 and 52 weeks. (Primary time point would be 52 weeks).

H3: Tai Chi is superior to Attention Control at 12, 26, and 52 weeks (assuming we include the AC group). (Primary time point would be 12 weeks).

The primary outcomes would be back-related dysfunction (most critical) and pain.

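### The printed outcome model has no Time main effect, so any change shared by all arms between follow-up visits biases the visit-specific contrasts with Usual Medical Care and the Trt x Time terms

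*Protocol*

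**What the plan says.** Protocol section 9.6 iii (Preliminary Outcome Analyses) sets out one GEE model for the outcome measures: "we will analyze outcomes from all follow-up time points in a single model". The right-hand side, after the intercept, reads "\beta_1 Baseline + \alpha_1 Trt + \alpha_2 Trt \times Time + \alpha_3 z", followed by an error term. The components are defined as follows.

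- **Trt:** these terms "include a dummy variables for the Tai Chi group or the Comprehensive Health Education Control group".
- **Referent:** "The referent group in this model is the Usual Medical Care group".
- **Time:** this "is a series of dummy variables indicating the follow-up times". It appears only inside the product with Trt.
- **z:** a vector of other adjustment variables. The adjusters named in the text are the baseline value, gender and age.

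On the interaction the section says "we will include an interaction term between treatment group and time point". The reason given is that constant or linear group differences over time cannot be assumed. The same section says of these analyses: "We will employ the analytic techniques we would propose in a full-scale trial". Section 2.2a gives the first full-trial hypothesis as "Tai Chi is superior to Usual Medical Care at 12, 26, and 52 weeks", with 12 weeks as the primary time point. The SAP contains no outcome model.

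**The concern.** For a UMC participant every Trt and Trt x Time column is zero, so nothing in the linear predictor changes from one visit to the next. The model allows UMC a single adjusted mean over 12, 26 and 52 weeks, while Tai Chi and Health Education are free at each visit. Two things follow if outcomes drift in all arms between those visits.

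- Each visit-specific contrast with UMC compares an arm at that visit with UMC averaged over visits.
- Each Trt x Time coefficient measures that arm's own change since the reference visit, not its change relative to UMC. The interaction was included to capture the latter.

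If all arms improve alike from 12 to 52 weeks, Tai Chi looks too weak at 12 weeks and too strong at 52, which imitates a growing or lasting benefit. Common worsening does the reverse. Of the full-trial hypotheses in section 2.2a, only H1 (Tai Chi versus UMC) is exposed.

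**Working it through.** **Inputs.** From the documents: the equation and coding in Protocol section 9.6 iii, visits at 12, 26 and 52 weeks, and arms of 39 (Tai Chi), 15 (Attention Control) and 24 (UMC) from the Precis. The documents state no SD, correlation or drift. I assume RMDQ SD 5 and correlation 0.6 between any two occasions, baseline included, and then vary both. D is the assumed common change from 12 to 52 weeks. There is no figure in the plan to reproduce.

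**Step 1: bias.** With balanced follow-up and an independence or exchangeable working correlation, the intercept estimates the three-visit UMC average. With no treatment effect:

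bias(t) = common time effect at t minus its mean over the three visits.

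- Equal steps (0, D/2, D; mean D/2): -0.50D, 0, +0.50D at 12, 26 and 52 weeks.
- Linear in weeks (0, 14/40 D = 0.35D, D; mean 1.35D/3 = 0.45D): -0.45D, -0.10D, +0.55D.
- All change by week 26 (0, D, D; mean 0.67D): -0.67D, +0.33D, +0.33D.

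Week 26 escapes only when the UMC mean there equals its three-visit average. An AR(1) working correlation alters the weights but does not remove the bias. The 52-week interaction (12 weeks as reference) is off by D in every pattern. Solving the model without noise with Time dummies added gives exactly zero for all of these.

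**Step 2: standard errors.** After baseline adjustment, the residual variance is v = 25(1 - 0.36) = 16 and the residual covariance between visits is c = 25(0.6 - 0.36) = 6.

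- Tai Chi minus UMC at a visit, as written: sqrt(v/39 + (v + 2c)/(3 x 24)) = sqrt(0.410 + 0.389) = 0.894.
- The same with Time: sqrt(16/39 + 16/24) = 1.038.
- Attention Control minus UMC: 1.206 as written, 1.317 with Time.
- Tai Chi x 52-week term, as written: sqrt(2(v - c)/39) = sqrt(20/39) = 0.716.

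**Step 3: false-positive rates, normal approximation.** Rate = Phi(-1.96 + b/SE) + Phi(-1.96 - b/SE), where b is the absolute bias. The first two columns are Tai Chi minus UMC contrasts.

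| D (points) | Equal steps, 12 or 52 weeks | Linear in weeks, 12 / 52 weeks | Tai Chi x 52-week term |
|---|---|---|---|
| 0.5 | 5.9% | 5.7% / 6.1% | 10.7% |
| 1 | 8.7% | 7.9% / 9.4% | 28.7% |
| 2 | 20.1% | 17.2% / 23.4% | 79.8% |

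Varying correlation over 0.4-0.8 at SD 5, or SD over 4-6 at correlation 0.6, and taking both drift shapes, the visit contrasts run from 7.0% (SD 6, 12 weeks) to 12.7% (correlation 0.8, 52 weeks) at 1 point, and from 13.4% to 36.3% at 2 points.

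**Step 4: simulation.** Exchangeable GEE with robust standard errors, 39/15/24, no treatment effect, 4,000 replicates per scenario, improvement in equal steps (lower RMDQ is better, so D is negative).

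| Drift | Mean Tai Chi minus UMC at 12/26/52 weeks | Rejection |
|---|---|---|
| 0.5 | +0.24 / 0.00 / -0.23 | 7.0 / 6.9 / 6.8% |
| 1 | +0.49 / 0.00 / -0.48 | 10.2 / 6.9 / 10.2% |
| 2 | +0.99 / 0.00 / -0.98 | 21.8 / 6.9 / 21.7% |
| With Time | bias 0.02 or less | 6.1 / 6.6 / 5.6% |

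- Linear in weeks: 9.5% and 11.0% (1 point), 19.3% and 24.5% (2 points) at 12 and 52 weeks.
- No drift, or a flat 2-point shift at all visits, as written: bias 0.02 or less and rejection 6.4-7.0%. That is the small-sample GEE baseline to compare against.
- Tai Chi x 52-week term: -0.47, -0.97 and -1.97 for drifts of 0.5, 1 and 2 points as written; +0.04 with Time.
- The visit-averaged Tai Chi minus UMC contrast and the Tai Chi minus Attention Control contrasts are the same in both models.

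**The case against.** The section gives only a general form, in loose notation: it sets an error term beside a link function. The prose describes the right idea, and most analysts fit an interaction with both main effects, so this may be a drafting slip that never reaches the code. The protocol also promises to test its analytic programs (section 10.2). The analyses are described as underpowered, section 3 disclaims effectiveness hypotheses, and no test or decision rule is attached, so false-positive rates describe a decision that this trial does not make. The bias needs the UMC mean to move between 12 and 52 weeks, and at a 0.5-point drift the simulated rejection for Tai Chi versus UMC (6.8-7.0%) is hardly above the no-drift level. The SAP covers feasibility analyses only.

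Much of this stands as a limit on weight: the bias is conditional, small drifts matter little for single-visit contrasts, and the feasibility conclusions are untouched. It does not rescue the equation. Time has its own definition and is not among the named adjusters. Trt is listed separately from Trt x Time, so the product cannot be read as full crossing. No other text in either document supplies the term. A programmer following the only model given would omit it, and testing the program against that model would not reveal the omission.

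**Conclusion.** The concern holds. As written, the model cannot give unbiased visit-specific contrasts with UMC unless the UMC mean is flat across the three follow-ups, and its interaction does not measure what the section says it should. The bias is about half the common 12-to-52-week change, in opposite directions at 12 and 52 weeks, and equals the whole change for the 52-week interaction. These bias results need no SD or correlation; the error rates do, and they rest on the assumed values and ranges above.

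A shift already present at 12 weeks and constant afterwards does no harm. No feasibility criterion is affected. The correction should still be made, because the section presents this as the method for the full-scale trial, where H1 is a visit-specific contrast with UMC.

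**What to change.** In Protocol section 9.6 iii, write the model as intercept + Baseline + Time + Trt + Trt x Time + z, with one follow-up visit named as the reference level for Time. Report each visit's arm contrasts from that model, and copy it into the SAP so that the outcome analysis is specified in both documents.

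The cost is one line of text and two parameters. In the simulation (SD 5, correlation 0.6) the standard error of a visit-specific Tai Chi minus UMC contrast rises from 0.87 to 1.01 RMDQ points, and that of Attention Control minus UMC from about 1.16 to 1.27. Standard errors for the visit-averaged and the Tai Chi minus Attention Control contrasts do not change. The loss of precision comes from dropping the assumption of a flat UMC mean, which the protocol does not justify.

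The change does not address cohort or calendar imbalance between arms (section 4.4 takes 19 of the 24 UMC participants from the first cohort), which is a separate matter.

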## **10. DATA COLLECTION, QUALITY CONTROL AND CONFIDENTIALITY**

## **10.1 Data Collection Forms**

Eligibility information will be collected directly in a computer assisted telephone interviewing database. Baseline and follow-up questionnaires will be self-report on paper forms or, if necessary, via telephone interview. Masked assessors (trained Research Specialists) will collect data on the physical assessments using paper forms.

Individual records will be identified by a unique study identification number.

Records linking study ID with participant names or other identifying information that may be needed for follow-up interviews, class attendance, etc. will be kept separate from the study data and will be accessed only by study team members on a need-to-know basis. All study files will be kept in a locked filing cabinet. Computer files will be secure and password protected.

## **10.2 Data Management**

We will employ our time- tested procedures for interview data collection and quality control, scanning self-administered forms or using double key entry verification of paper forms or to minimize data collection errors during baseline and follow-up interviews. If possible, self-report interview data will be collected in –person and inspected for completeness before the participant leaves to minimize errors. We will employ our standard quality control procedures to ensure that data collection is proceeding smoothly, electronic data are password protected and paper forms are stored in locked filing cabinets to ensure confidentiality of information.

We will implement procedures to ensure that all data collection processes are proceeding smoothly. These procedures will ensure that randomization is proceeding as planned, recruitment is on schedule, data collection forms are accurately entered into databases, the database is storing data correctly and that data can be accurately transferred and retrieved as needed. We will develop a relational database to track information on every stage of recruitment, randomization, class attendance, and outcomes assessment so we can report patient flow automatically and in an integrated fashion using standard, automated reports. All data system processes will be thoroughly tested prior to the start of recruitment.

All questionnaire databases will contain range and logic checks. Participant attendance information collected during the classes will be double key entered into a computer database that also contains logic checks. Prior to recruitment, all data systems will be tested with imaginary participants. Data will be examined for completeness using computer programs developed specifically for that purpose. In addition, we will test all analytic programs to ensure that the analyses are accurate. Computer files with participant names will be password protected with access restricted to staff using this information to recruit participants, contact class participants or obtain follow-up data, and interact with any patients reporting adverse events. Any paper data forms, such as homework logs, identifiable only by unique study ID numbers, will be kept in locked filing cabinets. Finally, all analysis data files will be password protected. Full data backup procedures are performed nightly, with partial data back-up throughout the day.

## **10.3 Quality Assurance**

### **10.3.1 Training**

All study staff will have had prior experience with RCTs, will have been trained in Good Clinical Practice Guidelines, and will be trained specifically on the procedures for this trial. A study Manual of Operations will be created that details the procedure for each element of the study implementation. Prior to the start of recruitment, the study team will participate in training sessions with mock participants to ensure an understanding of all study procedures and consistency in application.

### **10.3.2 Protocol Deviations**

Protocol deviations will be captured through weekly review of study recruitment and follow-up reports and through routine bi-weekly data checks of study data being collected, entered, and stored in our study databases. The weekly review of study recruitment and follow-up reports will be conducted by PI, [name] and Project Manager [name]. The bi-weekly data check of the study databases will be performed by the programmer and reviewed by PI [name] and Project Manager [name]. In addition, study staff responsible for conducting these activities will meet with Project Manager [name] on a weekly basis to discuss study progress and any potential violations that may have occurred. Protocol violations will be reported to the Kaiser Permanente Washington IRB as a part of the annual continuing review report. In addition, protocol violations will be reported to the Independent Monitoring Committee as a part of the reports completed every six months during active recruitment, intervention, and follow-up periods.

### **10.3.3 Monitoring**

Project Manager [name] will meet with study staff responsible for conducting RCT activities on a weekly basis to discuss and review recruitment, intervention and follow-up activities. A study data quality assurance (QA) tracking file will be created in EXCEL and will be used to track adherence to the study protocol. Examples of elements including on the QA tracking file are: confirmation of signed consent form, confirmation of home practice logs (for those randomized to Tai Chi), and attendance information. The study QA tracking file will be completed by our study research specialists and will be reviewed by Project Manager [name]. Any protocol deviations will be shared with PI [name] and will be reported to the Kaiser Permanente Washington IRB and our study DSMBody at the next regularly scheduled reporting period. In addition, our study programmer will run data QA checks to ensure that study data being collected is complete and accurate. Any abnormalities in data will be immediately reported to PI [name] and Project Manager [name] so that a solution can be created.

## **11. ETHICAL PRINCIPLES**

### **11.1 Institutional Review Board**

The investigators are responsible for obtaining initial and continuing review (at intervals of not less than yearly) of the study by their IRB. Written approval from the IRB will be on file prior to commencement of study activities. All study personnel have Human Subjects Research Training certification on file with the IRB, including Good Clinical Practice training

## **11.2 Informed Consent:**

Kaiser Permanente Washington members who are have received an invitation letter to the study and are interested in participating will sign and return a statement indicating their willingness to be contacted by study staff. A toll-free study line will also be included for potential participants who prefer to contact study staff via telephone. A Research Specialist will then phone interested enrollees to answer questions, obtain oral consent for an initial telephone eligibility screen and determine preliminary eligibility using a computer program to guide the interviewer through a series of screening questions. The screening process ends with documentation in a database of either preliminary eligibility or ineligibility. Once a potential participant has been deemed preliminarily eligible, they will be scheduled to attend one of our in-person group eligibility screening and assessment visits at a Kaiser Permanente Washington Medical Center. While the in-person visits are in a group setting, physical assessments, informed consent, and randomization will take place in a private room adjacent to the group area. During the group assessment visit, eligibility will be confirmed through completion of a final eligibility screening (e.g. demonstration of sufficient mobility, willingness to be randomized). If the participant is deemed eligible and is willing to participate, informed consent will be administered by a study Research Specialist. This will include an explanation of interview time commitments and content, intervention commitments (class attendance, home practice, and home practice diary completion), potential risks of participation, potential benefits of participation, what to do for an adverse event, and options for discontinuation of participation in the study. The Research Specialist will also explain the handling of data and personal health information as dictated by HIPAA. Signed consent forms will be kept at the Kaiser Permanente Washington Research Institute in a locked filing cabinet only accessible by the appropriate study staff.

## **11.3 Health Insurance Portability and Accountability Act (HIPAA)**

Kaiser Permanente Washington has instituted a protocol that ensures research is conducted in compliance with the federal law entitled, "Health Insurance Portability and Accountability Act (HIPAA)". Permission to use, create, and release personal health information for research will be obtained before potential participants can be enrolled in this study. One of the study Research Specialists will explain HIPPA as it relates to this research study to potential participants to ensure that they understand it and have the opportunity to ask any questions pertaining to their personal health information as it relates to this study. This process will explain what is meant by health information, how health information is obtained, how the researchers may use health information, and detail the steps a participant must take if s/he decides to revoke this permission.

## **11.4 Confidentiality of Participant Records**

The investigators and their study teams will maintain strict confidentiality of the participant records. Individual records will be identified by a unique study identification number. Records linking study ID with participant names or other identifying information that may be needed for follow-up interviews, class attendance, etc. will be kept separate from the study data and will be accessed only by study team members on a need-to-know basis. All study files will be kept in a locked filing cabinet. Computer files will be

secure and password protected. Any information about any participant will not be released without the written permission of the participant, except as necessary for monitoring by the KPW IRB, the NCCIH and the OHRP.

